2.4. Study Procedures

Patients participating in this study will complete 7 scheduled visits for a total study duration of up to 8 weeks (including Screening period). The study will involve a Screening period (up to 14 days), a Baseline/Day 1 visit (Day 1) and 5 outpatient visits following Day 1. At each visit following Screening, patients will provide blood samples for TA drug concentration measurements for PK analysis.

At specified times throughout the study, patients will undergo safety assessments such as physical examinations, vital signs, hematology and chemistry blood collection for analyses and, adverse event and concomitant medication review.

Blood samples for TA drug concentration measurements will be obtained from all patients prior to administration of study medication on Day 1, and at hours 1, 2, 3, 4, 5, 6, 8, 10, and 12 (\pm 10 minutes) after the first knee injection, on Day 2 at 24 hours (\pm 2 hours) after the first injection of study medication, and at each of the subsequent scheduled visits: Day 8, 15, 29 and 43 (time as

convenient during the scheduled visit). The date and time that each blood sample was obtained will be recorded.

Blood samples for morning cortisol levels will be obtained between 7-9 am from all patients at Screening, prior to administration of the study medication on Day 1, and then at each of the subsequent scheduled visits.

The schedule of assessments, as outlined in the study protocol, is provided in Table 1

Table 1 Schedule of Assessments

Procedures	Screening ¹	Day 1	Day 2	Day 8 ²	Day 15 ²	Day 29 ²	Day 43 ² (End of Study)
Informed consent	X ³						
Inclusion/Exclusion Review	X	X ⁴					
Medical History/Update	X	X ⁴					
OA Medical History	X						
Prior Treatment & Medications ⁵	X	X ⁴					
Physical Examination	X	X ⁴					X
Bilateral Knee X-rays	X ⁶						
Bilateral Knee Assessments ⁷	X	X ⁴					X
12-Lead ECG	X						
Vital Signs	X	X ⁴	X	X	X	X	X
Height	X						
Weight and BMI	X						X
Hematology & Chemistry ⁸	X	X ⁴					X
HIV, Hepatitis B/C, HbA1c ⁸	X						
Pregnancy Test ⁹	X	X ⁴					X
Blood for Drug Concentrations		X ¹⁰	X ¹¹	X	X	X	X
Blood for Morning Serum Cortisol ¹²	X	X ⁴	X	X	X	X	X
Knee Aspiration and Collection of Synovial Fluid		X ⁴					
Treatment Administration ¹³		X					
Adverse Event Monitoring ¹⁴		-----	-----	X	-----	-----	-----
Concomitant Medications ¹⁴		-----	-----	X	-----	-----	-----

1 Screening may occur up to 14 days prior to Day 1 (calendar day of dosing).

2 Visit should be conducted +/- 2 days from scheduled date

3 Consent must be obtained prior to performing any study-specific procedures.

4 Complete assessment prior to dosing.

5 Record any medications received within 30 days prior to Screening.

6 Obtain new x-rays if >6 months since prior x-ray.

7 Both knees will be assessed for tenderness, heat/redness, swelling, effusion, and Baker's cyst. Clinically significant findings (new or worsening from baseline) should be recorded as AEs.

8 Via Central Laboratory

- 9 Conduct for females of childbearing potential only. Serum pregnancy test to be performed via central laboratory at Screening and End-of-Study visit (scheduled for Day 43); urine pregnancy test to be performed locally on Day 1 and results available prior to dosing.
- 10 On Day 1, blood for plasma drug concentration measurements will be collected prior to dosing and at Hours 1, 2, 3, 4, 5, 6, 8, 10, and 12 post-injection of the first knee (\pm 10 minutes).
- 11 On Day 2, blood for plasma drug concentration measurements will be collected at 24 hours post-injection of the first knee (\pm 2 hours), and on subsequent visits as convenient.
- 12 Blood for morning cortisol measurements will be collected between 7 and 9 am.
- 13 The injection of the second knee should take place within 15 minutes of the first knee injection.
- 14 AEs and Concomitant Medications will be captured from Day 1 (post-injection) to End of Study Visit.

2.5. Safety, Pharmacodynamic and Pharmacokinetic (PK) Safety Variables

2.5.1. Safety Variables

Safety and tolerability will be evaluated on the basis of AEs spontaneously reported by the patient or discovered by the Investigator and, findings from the following assessments: physical examinations, knee assessments, vital signs, and clinical laboratory evaluations.

2.5.2. Pharmacokinetic Variables

Blood samples (4 mL per sample) for TA drug concentration measurements will be obtained from all patients at the following nominal, or planned, times:

- On Day 1, within 1 hour prior to administration of study medication (Nominal Time -1),
- On Day 1, at Hours 1, 2, 3, 4, 5, 6, 8, 10, and 12 (\pm 10 minutes) after injection of the first knee,
- On Day 2, at 24 (\pm 2 hours) after injection of the first knee,
- On Days 8, 15, 29, and 43 (time as convenient during the scheduled visit).

These represent a total of 15 samples from each patient, each sample representing 4 mL of blood, for a maximum estimated total volume of 60 mL of blood collected from each patient for drug concentration measurement.

Procedures for sample collection, handling, storage and shipment will be described in the Laboratory Manual. Plasma TA concentrations will be measured using an established validated LC-MS/MS method.

PK parameter endpoints are described in section 4.8.4.

2.5.3. Pharmacodynamic Variables

Blood samples for serum cortisol levels will be collected between 7 am and 9 am at Screening, prior to administration of the study medication on Day 1, and on Study Days 1, 2, 15, 29, 43.

Synovial fluid samples will be preserved for a maximum of 5 years for potential future analyses of biomarkers that may have utility in defining pathogenesis of OA and/or be associated with responsiveness to FX006 treatment. No analysis is planned at this time.

3. PATIENT POPULATIONS

3.1. Population Definitions

The following patient populations will be evaluated and used for presentation and analysis of the data:

Safety population:

All patients who received study medication (injection in at least one knee). Patients will be analyzed according to the treatment they have received (“analyses as treated”).

Pharmacokinetic Population:

All patients from safety population who receive two IA injections (one to each knee), complete scheduled sampling, and have sufficient plasma concentration data to allow calculation of PK parameters will be included in the PK population. Review of the plasma drug concentration data and eligibility for inclusion into the PK population will be completed by the study Pharmacokineticist. The rationale for inclusion or exclusion in the PK population will be documented and listed. Patients will be analyzed according to the treatment they have received (“analyses as treated”).

3.2. Protocol Deviations

All protocol deviations will be presented in the data listings.

4. STATISTICAL METHODS

4.1. Sample Size Justification

4.1.1. Sample Size Considerations

In this study, it is expected that the systemic exposure in plasma of TA from extended-release FX006 should not exceed that of the immediate-release TAcS formulation for the key parameters of C_{max} , $AUC_{(0-t)}$, and $AUC_{(0-inf)}$.

In a previous PK study with knee OA patients (FX006-2015-009) the ratio of the mean exposure parameters for FX006 32 mg (N=60) and TAcS 40 mg (N=18) for C_{max} was 0.10 with the upper limit of its 90% CI being 0.15 and for $AUC_{(0-inf)}$ was 0.52 with the upper limit of its 90% CI being 0.86. The pooled coefficients of variation for the parameters was between 0.53 (C_{max}) and 0.68 (AUC_{0-inf}).

4.1.2. Sample Size Estimate

In this study, it is expected that the ratio of exposure means (FX006/TAcS) will be less than 1.0 when administered to treat bilateral knee OA. A sample size of 12 in each treatment arm (24 in total) is estimated. The sample size of 24 achieves approximately 90% power, with a two-sided alpha 0.05, to detect a ratio less than 1.0 of the exposure PK parameter means (FX006 / TAcS), with a pooled coefficient of variation estimate of 0.68 (PASS 15 Power Analysis and Sample Size Software (2017). NCSS, LLC. Kaysville, Utah, USA, ncss.com/software/pass). The sample size of 12 per treatment arm assumes a 10% noncompliance sampling rate (a drop-out rate) for providing complete blood samples for PK analysis, and is sufficient to characterize the comparative PK of FX006 and TAcS in this study. The total sample size is estimated to be 24 patients (12 in each treatment arm) for the study.

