9.3. Determination of Sample Size

9.3.1. Sample Size Considerations

In this study, it is expected that the systemic exposure in plasma of TA from extended-release FX006 should not exceed that of the immediate-release TAc formulation for the key parameters of C_{max} , $AUC_{(0-t)}$, and $AUC_{(0-inf)}$.

In a previous pharmacokinetic study with knee OA patients (FX006-2015-009) the ratio of the mean exposure parameters for FX006 32 mg (N=60) and TAc 40 mg (N=18) for C_{max} was 0.10 with the upper limit of its 90% CI being 0.15 and for $AUC_{(0-inf)}$ was 0.52 with the upper limit of its 90% CI being 0.86. The pooled coefficients of variation for the parameters was between 0.53 (C_{max}) and 0.68 (AUC_{0-inf}).

9.3.2. Sample Size Estimate:

In this study, it is expected that the ratio of exposure means (FX006/TAc) will be less than 1.0 when administered to treat bilateral knee OA. A sample size of 12 in each treatment arm (24 in total) is estimated. The sample size of 24 achieves approximately 90% power, with a two-sided alpha 0.05, to detect a ratio less than 1.0 of the exposure PK parameter means (FX006 / TAc), with a pooled coefficient of variation estimate of 0.68 (PASS 15 Power Analysis and Sample Size Software (2017). NCSS, LLC. Kaysville, Utah, USA, ncss.com/software/pass). The sample size of 12 per treatment arm assumes a 10% noncompliance sampling rate (a drop-out rate) for providing complete blood samples for PK analysis, and is sufficient to characterize the comparative pharmacokinetic of FX006 and TAc in this study. The total sample size is estimated to be 24 patients (12 in each treatment arm) for the study.

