4.2.7. Discontinuations and Loss to Follow-up

Each treated patient from this study receives study medication as two single IA injections. Therefore, discontinuation from treatment is not applicable. Whether or not patients may receive the entire content of study drug injection will be considered in the study drug exposure analyses.

Each patient may only discontinue from the study for further assessments and study visits. Data collected from discontinued patients will be included in the CSR. Patients who discontinue from the study may be replaced at the discretion of the sponsor.

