$AUC_{(0-t)}$	Exposure: Area Under the Plasma Curve from time 0 to the last quantifiable concentration (t). Calculated using the linear trapezoidal rule.
$AUC_{(0-24)}$	Exposure: Area Under the Plasma Curve from time 0 to 24 hours post IA injection. Calculated using the linear trapezoidal rule
$AUC_{(0-\infty)}$	Exposure: Area Under the Plasma Curve from time 0 extrapolated to infinity. Calculated as follows: $AUC_{inf} = AUC_{(0-t)} + \frac{C_{last}}{\lambda_z}$ where C_{last} is the last quantifiable concentration.
CL	Total Body Clearance, computed as Dose/ $AUC_{(0-\infty)}$
MRT	Mean residence time extrapolated to infinity, computed as $AUMC_{(0-\infty)}/AUC_{(0-\infty)}$
Vz_F	Volume of Distribution, based on terminal phase, computed as : $\frac{Dose}{\lambda_z \cdot AUC_{(0-\infty)}}$

Descriptive summaries of the individual patient PK parameters and population summaries over all patients will be presented. Individual linear-linear and log-linear concentration profiles will be completed for each patient. Graphical display (plasma drug concentration curves) will be used to present geometric mean with 95% CIs for plasma drug concentrations (linear-linear and log-linear plots) for each treatment arm.

All PK parameters and data will be presented in a data listing. Results from the PK analysis will be included in the CSR. Along with the bioanalytical report from the assay laboratory, model output from the NCA analysis will be provided in a separate document.

A linear model will be used to compare the PK parameters from extended-release FX006 and immediate-release TAcS for each C_{max} , T_{max} , C_{last} , MRT, and AUC parameters. The model will include treatment as a single fixed effect. The least square mean difference (LSMD) between the two treatments will be explored to examine the magnitude of difference in exposure PK parameters between FX006 and TAcS. All p-values will be considered informative.

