4.8.5. Exploration of Bioequivalence between FX006 and TAcS

Bioequivalence (BE) ratios between extended-release FX006 (Test) and immediate-release TAcS (Reference) for C_{max} and AUC parameters will be explored. Bioequivalence between Test and Reference will be evaluated using the average BE method for the mean ratio between test and reference products ($\mu T / \mu R$) as described in FDA guidance for the assessment of bioequivalence (FDA, 2013).

The FDA Guidance on the assessment of Bioequivalence recommends that bioequivalence measures of AUC and C_{max} be log-transformed. In this study, the natural log will be used to transform the values for the model, and the C_{max} , AUC_{0-24} , and $AUC_{0-\infty}$. PK parameters will be exponentiated from a mixed effects model to examine bioequivalence.

In this study bioequivalence is not expected for the ratio of FX006 / TAcS. The properties of FX006 suggest that a reduced C_{max} (reduced maximum exposure) is evident due to slower release of TA into systemic circulation. The potential shift in T_{max} and potential decay in C_{max} , both of which would be associated with corresponding differences in AUC will be explored.

A linear mixed effects model may be used for this study to average bioequivalence with PK parameters of log-transformed AUC_{0-24} , $AUC_{0-\infty}$, and C_{max} . In the initial model fixed effects for treatment and site will be included, with a random effect for patient.

GM with 95% CIs will be presented for each treatment group. BE ratio with standard error (SE) and 90% CIs will be presented for C_{max} , AUC_{0-24} , and $AUC_{0-\infty}$.

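### The 90% power claim names no ratio; with the plan's own AUC(0-inf) figures (ratio 0.52, CV 0.68), power is about 70% at 12 per arm or 66% at 11

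*SAP*

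**What the plan says.** SAP 4.1.1 names Cmax, AUC(0-t) and AUC(0-inf) as the key exposure parameters. From an earlier single-knee study (60 patients on FX006 32 mg, 18 on TAcS 40 mg) it quotes a Cmax ratio of 0.10 (upper 90% limit 0.15) and an AUC(0-inf) ratio of 0.52 (upper 90% limit 0.86). On variability it says: "The pooled coefficients of variation for the parameters was between 0.53" for Cmax and 0.68 for AUC(0-inf).

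SAP 4.1.2 then claims: "The sample size of 24 achieves approximately 90% power, with a two-sided alpha 0.05, to detect a ratio less than 1.0", for the exposure parameter means in general and with the CV of 0.68. The 12 per arm "assumes a 10% noncompliance sampling rate (a drop-out rate"). Protocol 9.3.2 and the synopsis make the same claim ("The sample size of 24 achieves approximately 90% power").

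Three other places bear on how to read it:
- SAP 4.8.4 compares the arms with a linear model that has treatment as its only effect. It names no transformation and adds: "All p-values will be considered informative".
- SAP 4.8.5, on bioequivalence, gives the log scale: "In this study, the natural log will be used to transform the values for the model".
- SAP 4.2.7 makes replacement optional: "Patients who discontinue from the study may be replaced at the discretion of the sponsor".

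**The concern.** A power figure needs a specific alternative. With N, alpha and CV fixed, power can take almost any value depending on the true ratio, and the text gives only a direction. The test and the analysis scale are also missing from the sample-size text.

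A reader who fills the gap from the documents has one natural choice. The CV of 0.68 belongs to AUC(0-inf), so the matching ratio is 0.52, and that pair does not give 90%.

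Comparing systemic exposure is a primary objective, and AUC(0-inf) is one of the three key parameters. P-values are only informative and bioequivalence is exploratory, so no formal conclusion fails. The risk lies in interpretation: an AUC(0-inf) interval that includes 1.0 would be taken as the result of a 90%-powered comparison. SAP 1.2 says these analyses will feed the study report, regulatory filings and manuscripts.

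**Working it through.** **Inputs.** From SAP 4.1.1 and 4.1.2: two-sided alpha 0.05, 12 per arm, CV 0.68, AUC(0-inf) ratio 0.52, Cmax ratio 0.10 with CV 0.53, and 10% loss. Without replacement the loss leaves 12 × 0.9 = 10.8, about 11 per arm. Assumed here: null ratio 1.0, two-sample t-test, log scale (the scale SAP 4.8.5 uses for ratios).

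**Trying to reproduce the 90%.** No ratio is given, so the calculation can only be run backwards. At CV 0.68, 90% power corresponds to a true ratio of 0.426 (12 per arm) or 0.408 (11 per arm). Neither value appears in the documents.

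**AUC(0-inf) with the documented pair.**
- Log-scale SD: σ = √ln(1 + 0.68²) = √0.3801 = 0.6165.
- Effect: ln(0.52) = −0.654.
- Noncentrality: |effect| / (σ√(2/n)).
  - n = 12: 0.654 / 0.2517 = 2.60, 22 df, critical value 2.074. **Power 70.0%.**
  - n = 11: 0.654 / 0.2629 = 2.49, 20 df, critical value 2.086. **Power 65.8%.**

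Simulation of lognormal data (200,000 runs) gave 69.8% and 65.9%.

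**How far the result moves.**

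| Variant | 12 per arm | 11 per arm |
|---|---|---|
| Rounding (ratio 0.515–0.525, CV 0.675–0.685) | 68–72% | 64–68% |
| True ratio 0.60 | 49% | 46% |
| One-sided 0.05 (text says two-sided) | 81% | 78% |
| Untransformed, SD = 0.68 × each arm's own mean | 55% | 51% |
| Untransformed, SD = 0.68 × average of the two means | 59% | 55% |
| Untransformed, SD = 0.68 × TAcS mean in both arms | 38% | 35% |
| Untransformed, SD = 0.68 × FX006 mean in both arms | 89% | 86% |

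The SDs in the untransformed rows are assumptions. The last row comes close to 90% only by giving TAcS a CV of 0.68 × 0.52 = 35%, which is not a pooled 0.68.

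At ratio 0.52, 90% would need a CV of 0.50 or lower (12 per arm) or 0.47 or lower (11 per arm), or else 20 evaluable patients per arm at CV 0.68.

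**Cmax.** With ln(0.10) and CV 0.53, log-scale power exceeds 99.9% at either size. For AUC(0-t) the documents give neither a ratio nor a CV, so no power can be computed.

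**The case against.** The best defence is that 0.52 was never declared as the design alternative. SAP 4.1.1 reports it as an earlier single-knee result, and SAP 4.1.2 says only that the ratio should be below 1.0. On that view the 90% is unverifiable rather than wrong, and it would be true at a ratio near 0.43. This is right as far as it goes: the sponsor may have used another ratio. But no other AUC(0-inf) ratio is available to a reader, so the claim is unsupported until one is stated.

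The null is also inferred. Against an upper bound of 1.25, ratio 0.52 and CV 0.68 give 91.5% (12 per arm) and 88.7% (11 per arm), close to the stated figure. No such bound appears in the documents, and the wording "with a two-sided alpha 0.05, to detect a ratio less than 1.0" points to a null of 1.0.

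The 66–70% may itself be too precise. With 60 and 18 patients, a log SD of 0.6165 implies an upper 90% limit of 0.52 × exp(1.665 × 0.6165 × √(1/60 + 1/18)) ≈ 0.69, not the quoted 0.86. If 0.86 came from a simple two-group log-scale comparison (an assumption), the log SD would be about 1.12, the CV about 1.6, and power only about 28% or 25%. So the quoted ratio, limit and CV do not fit together under that reading. This stands, and it points to lower power.

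Two smaller points also stand. Replacement is permitted, so 11 per arm is not certain. And the Cmax figure depends somewhat on scale: with a constant untransformed SD of 0.53 × the TAcS mean it is about 98% or 97%.

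**Conclusion.** The concern holds. The power statement names no alternative, and the one matched pair of AUC(0-inf) inputs in the documents gives about 70% (12 per arm) or 66% (11 per arm), some 20 to 24 points below the stated 90%. This rests on a null ratio of 1.0, a log-scale two-sample t-test at two-sided 0.05, and the earlier study's ratio and CV carrying over to bilateral dosing. The variants that come near 90% depart from the stated inputs or add one the documents do not contain.

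The shortfall is confined to AUC(0-inf). It should be corrected, but it does not invalidate the design or any planned analysis.

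**What to change.** Keep 24 patients. Replace the power sentence in SAP 4.1.2, Protocol 9.3.2 and the synopsis with:

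> With 12 (11) evaluable patients per arm, a two-sided 0.05 two-sample t-test on log-transformed values against a null ratio of 1.0 has power above 99% for Cmax (ratio 0.10, CV 0.53) and about 70% (66%) for AUC(0-inf) (ratio 0.52, CV 0.68). Power for AUC(0-inf) reaches 90% only if the true ratio is about 0.43 (0.41) or lower. No power is claimed for AUC(0-t).

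If the software run used a different ratio, null or scale, state those inputs and the power they give instead. Either way, state the scale and method behind the earlier study's confidence limits and pooled CVs, so that the 0.86 limit and the 0.68 CV can be reconciled and the calculation repeated.

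The cost is wording in three places and a less favourable stated power for AUC(0-inf). No patients are added and no analysis changes.

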4.2. General Statistical Methods and Data Handling

4.2.1. General Methods

All output will be incorporated into Microsoft Excel or Word files, sorted and labeled according to the International Conference on Harmonization (ICH) recommendations, and formatted to the appropriate page size(s).

Tabulations will be produced for appropriate demographic, baseline, pharmacodynamics, PK and safety parameters. Summary tables will present data by treatment arm.

For categorical variables, summary tabulations of the number and percentage within each category (with a category for missing data) of the parameter will be presented.

For continuous variables, the number of non-missing values (n), the mean, median, standard deviation (SD), minimum and maximum values will be presented. 95% Confidence Intervals (CI) may be provided. In addition, for concentration-based parameters, the coefficient of variation (CV %), the geometric mean (GM) and log-scale standard deviation will be provided. Additional statistics may be presented for certain endpoints as described below.

All collected data will be presented in by-patient listings sorted by treatment arm and patient number.

All data listings that contain an evaluation date will contain relative analysis day (Rel Day). Pre-treatment and post treatment analysis days are numbered relative to the day of the first dose of study treatment (i.e., injection in the first knee), which is designated as Day 1. The preceding day is Day-1; the day before that is Day-2, etc.

For data listings relative to PK assessments where several assessments are made on the same day, there will be also a relative study day and time.

The sections below describe the intended analysis of the endpoints. Additional sensitivity analysis may be employed in the event of any unforeseen data anomalies or data issues not known at the time of writing this analysis plan.

4.2.2. Computing Environment

All descriptive statistical analyses will be performed using SAS® statistical software (Version 9.4 or higher), unless otherwise noted.

Non-compartmental PK analyses (NCA) will be conducted using Phoenix 7, WinNonlin® Version 7 or higher (Certara Corporation).

Adverse events will be coded using Medical Dictionary for Regulation Activity (MedDRA) Version 20.1 (or higher).

Concomitant medications will be coded using World Health Organization (WHO) Drug Dictionary (DD) (Version B3 Mar 2014 or Higher).

